6.3 STUDY INTERVENTION COMPLIANCE

A compliance assessment will be recorded at Visit 1, Visit 2, and Visit 3. The study staff will ensure that the subject has the headphones appropriately placed on the ears for 10 minutes continuously while the sound is being played and will record this compliance at the end of each session in the Case Report Form (CRF). In the event that the subject is unable to complete the 10-minute period, the staff will remove the headphones, provide the subject with a 30-minute break, then reattempt the 10-minute auditory intervention. If not successful, the subject will be removed from the study and an additional subject will be added.

7 STUDY INTERVENTION DISCONTINUATION AND PARTICIPANT DISCONTINUATION/WITHDRAWAL

7.1 DISCONTINUATION OF STUDY INTERVENTION

Discontinuation from the study intervention does not mean discontinuation from the study, and remaining study procedures should be completed as indicated by the study protocol. If a clinically significant finding is identified (including, but not limited to changes from baseline) after enrollment, the investigator or qualified designee will determine if any change in participant management is needed. Any new clinically relevant finding will be reported as an AE.

The data to be collected at the time of study intervention discontinuation will include the administration of all end of study outcome measures, if possible.

7.2 PARTICIPANT DISCONTINUATION/WITHDRAWAL FROM THE STUDY

Participants are free to withdraw from participation in the study at any time upon request.

An investigator may discontinue or withdraw a participant from the study for the following reasons:

- Significant study intervention non-compliance
- If any clinical AE or other medical condition or situation occurs such that continued participation in the study would not be in the best interest of the participant
- Disease progression which requires discontinuation of the study intervention (development of neuropsychiatric symptoms of dementia)
- If the participant meets an exclusion criterion (either newly developed or not previously recognized) that precludes further study participation

The reason for participant discontinuation or withdrawal from the study will be recorded on CRFs. Subjects who sign the informed consent form and are randomized but do not receive the study intervention may be replaced. Subjects who sign the informed consent form, and are randomized and receive the study intervention, and subsequently withdraw, or are withdrawn or discontinued from the study, will not be replaced.

7.3 LOST TO FOLLOW-UP

A participant will be considered lost to follow-up if he or she fails to return for any of the scheduled visits and is unable to be contacted by the study site staff.

The following actions must be taken if a participant fails to return to the clinic for a required study visit:

- The site will attempt to contact the participant and the study partner to reschedule the missed visit and
 counsel the participant and the study partner on the importance of maintaining the assigned visit schedule
 and ascertain if the participant wishes to and/or should continue in the study.
- Before a participant is deemed lost to follow-up, the investigator or designee will make every effort to regain contact with the participant and the study partner (where possible, 3 telephone calls and, if necessary, a certified letter to the participant's last known mailing address or local equivalent methods).
 These contact attempts will be documented in the participant's study file.
- Should the participant and the study partner continue to be unreachable, the participant will be considered to have withdrawn from the study with a primary reason of lost to follow-up.

8 STUDY ASSESSMENTS AND PROCEDURES

8.1 EFFICACY ASSESSMENTS

Eligibility Criteria

Eligibility Criteria will be established by the PI using a clinical interview with the subject and informant to establish the NINCDS-ADRDA Alzheimer's Criteria for possible and probable AD and the DSM-V Diagnosis of AD or other type of dementia, the review of medical records, and cognitive assessment using the MMSE.

Clinical Global Impression of Change

CGIC scales have been used extensively as primary outcomes in phase 2 and 3 clinical trials for AD, mild cognitive impairment, and for cognitive enhancers. A CGIC score is intended to be used as a measure of clinically meaningful change, as distinct from an instrument's ability to assess any change. The ADCS-CGIC, the Alzheimer's Disease Cooperative Study - Clinical Global Impression of Change is the most commonly used process for obtaining an assessment of clinically meaningful change in clinical trials. The ADCS-CGIC is a systematic method for assessing clinically significant change in a clinical trial as viewed by an independent skilled and experienced clinician. The ADCS-CGIC requires the assessor to consider a number of cognitive, functional, and behavioral areas prior to providing an overall "global" assessment of clinical change. It was designed in response to an FDA request and on the basis of a survey of Alzheimer Disease Cooperative Study clinicians. It is performed by interviewing the patient to assess function and mental status and the informant, using a worksheet that comprehensively lists relevant symptoms potentially useful in judging clinically meaningful change, and allows for notes for future reference- it takes approximately 20 minutes per interview.

The Stanford Sleepiness Scale

The SSS was developed by Dement and colleagues in 1972 and is a one-item self-report questionnaire measuring levels of sleepiness throughout the day. The scale, which can be administered in 1-2 minutes, is generally used to track level of arousal at each hour of the day. The scale has been validated for adult populations aged 18 and older. The SSS is used in both research and clinical settings to assess the level of intervention or effectiveness of a specific treatment in order to compare a client's progress.

The Severe Impairment Battery (8-item)

The SIB evaluates cognitive abilities at the lower end of the range. There are 40 items, and it takes approximately 20 minutes to complete. It is composed of very simple one-step commands which are presented in conjunction with gestural cues. Example questions include:

- 'What's your name?'
- 'Please write your name here'
- 'What do you call the thing you drink coffee from?'

The SIB is divided into scorable subscales, each sampling within the range expected of the severely-impaired individual. The six major subscales are attention, orientation, language, memory, visuospatial ability and construction. There are also brief evaluations of praxis and the patient's ability to respond appropriately when his/her name is called (orienting to name). In addition, there is an assessment of social interaction skills.

The range of possible scores is 0-100. There is no cut-off for normal as the test should only be used with patients known to be severely impaired. However, it is possible to grade the severity of impairment by rating those who score less than 63 on the SIB (corresponding to less than 4 on the MMSE) as 'very severely impaired'. A recently derived 8-item version of the SIB — the SIB-8 — which takes about 3 minutes to administer, may represent a more convenient tool for use in clinical practice. Very good internal consistency/agreement and strong correlations between the SIB and the more rapid and convenient SIB-8 indicate that the SIB-8 may be a useful and efficient clinical proxy for the full SIB in evaluating treatment response in patients with advanced AD.

8.2 SAFETY AND OTHER ASSESSMENTS

NINCDS-ADRDA Alzheimer's Criteria for possible and probable AD research diagnosis

• The PI or another qualified investigator will apply the NINCDS-ADRDA Alzheimer's criteria to make a research diagnosis of the subject's AD status as possible or probable AD.

Diagnostic and Statistical Manual of Mental Disorders, Fifth Edition (DSM-V) research diagnosis

• The PI or another qualified investigator will apply the DSM-V criteria to make a research diagnosis of the subject's AD status.

Mini-Mental State Exam (MMSE)

 The MMSE will be performed with the subject and assesses orientation, immediate and delayed recall, concentration, language, and construction skills on a 0-30 scale of correctness. An MMSE score between 5-20 indicates subject eligibility.

Auditory Assessment

 An audiologist will perform pure-tone audiometry, where the subject will be instructed to raise their hand (or point to the appropriate ear) when they hear a tone.

Vital signs

• Vital signs (i.e. sitting pulse and sitting blood pressure) will be obtained by trained study personnel.

Timed Up and Go (TUG) Test

 The TUG Test measures the time (in seconds) taken for an individual to stand up from a standard armchair, walk 10 feet, turn, walk back to the chair, and sit down. It is a commonly used scale for measuring functional mobility and risk of falls.

MRI Metal Screening Questionnaire

• The MRI Metal Screening Questionnaire will be performed to determine if the subject has any metal items in their body that may be harmful in the scanner or may interfere with the MRI examination.

Recording of AEs and SAEs

See Section 8.4 for AE and SAE recording and classification.

Assessment of intervention adherence

 A compliance assessment will be recorded at Visit 1, Visit 2, and Visit 3. The duration of time that the subject adheres to the established procedures of the intervention will be logged during each visit on a CRF.

Functional Network Analysis

MRI scanning includes collection of a high-resolution T1-weighted MPRAGE (TR=2.3s, TE=2.23ms, flip angle=8°, 192 sagittal slices, FOV=256x256mm), followed by a 10-minute resting state fMRI scan and two 10-minute stimulation scans (nature sounds/preferred music; acquisition parameters: 3 mm³ voxels, TR=1.1s, TE=30 ms, flip angle=65°, 51 axial slices, matrix=64x64, 375 time points, acceleration factor=3). Gradient field maps will also be collected. More information about fMRI resources will be provided upon request.

8.3 ADVERSE EVENTS AND SERIOUS ADVERSE EVENTS

8.3.1 DEFINITION OF ADVERSE EVENTS

AEs are any untoward medical occurrences associated with the use of an intervention in humans, whether or not considered intervention-related (21 CFR 312.32 (a)). AEs the PI deems related to study procedures, related to the

study intervention, and/or medically important for an individual participant, regardless of causality, will be tracked during this study.

8.3.2 DEFINITION OF SERIOUS ADVERSE EVENTS

An AE or suspected adverse reaction is considered "serious" if, in the view of the PI, it results in any of the following outcomes: death, a life-threatening AE, inpatient hospitalization or prolongation of existing hospitalization, or a persistent or significant incapacity or substantial disruption of the ability to conduct normal life functions. Important medical events that may not result in death, be life-threatening, or require hospitalization may be considered serious when, based upon appropriate medical judgment, they may jeopardize the patient or subject and may require medical or surgical intervention.

8.3.3 CLASSIFICATION OF AN ADVERSE EVENT

SEVERITY OF EVENT

For AEs not included in the protocol defined grading system, the following guidelines will be used to describe severity.

- Mild Events require minimal or no treatment and do not interfere with the participant's daily activities.
- **Moderate** Events result in a low level of inconvenience or concern with the therapeutic measures and cause some interference with daily activities.
- **Severe** Events incapacitate a participant in daily activities and may require systemic drug therapy or other treatment. Of note, the term "severe" does not necessarily equate to "serious".

RELATIONSHIP TO STUDY INTERVENTION

All AEs must have their relationship to the study intervention assessed by the PI who examines and evaluates the participant based on temporal relationship and his/her clinical judgment. The degree of certainty about causality will be graded using the categories below. In a clinical trial, the study intervention must always be suspect.

- Related The AE is known to occur with the study intervention, there is a reasonable possibility that the
 study intervention caused the AE, or there is a temporal relationship between the study intervention and
 event. Reasonable possibility means that there is evidence to suggest a causal relationship between the
 study intervention and the AE.
- Not Related There is not a reasonable possibility that the administration of the study intervention
 caused the event, there is no temporal relationship between the study intervention and event onset, or
 an alternate etiology has been established.

EXPECTEDNESS

The PI will be responsible for determining whether an AE is expected or unexpected. An AE will be considered unexpected if the nature, severity, or frequency of the event is not consistent with the risk information previously described for the study intervention.

8.3.4 TIME PERIOD AND FREQUENCY FOR EVENT ASSESSMENT AND FOLLOW-UP

The occurrence of an AE or SAE may come to the attention of study personnel during study visits and interviews of a study participant.

All AEs not meeting the criteria for SAEs will be captured on the appropriate CRF. Information to be collected includes event description, time of onset, PI's assessment of severity, relationship to study intervention (assessed only by those with the training and authority to make a diagnosis), and time of resolution/stabilization of the

event. All AEs occurring during the course of the study must be documented appropriately regardless of relationship. All AEs will be followed to adequate resolution.

Any medical condition that is present at the time that the participant is screened will be considered as baseline and not reported as an AE. However, if the study participant's condition deteriorates at any time during the study, it will be recorded as an AE.

Changes in the severity of an AE will be documented to allow an assessment of the duration of the event at each level of severity to be performed. AEs characterized as intermittent require documentation of onset and duration of each episode.

The study coordinator will record all reportable events with start dates occurring any time after informed consent is obtained until 7 (for non-serious AEs) or 30 days (for SAEs) after the last day of study participation. At each study visit, the investigator will inquire about the occurrence of AE/SAEs since the last visit. Events will be followed for outcome information until resolution or stabilization.

8.3.5 ADVERSE EVENT AND SERIOUS ADVERSE EVENT REPORTING

The PI will monitor the study procedures for this trial for overall safety and scientific relevance on an ongoing basis. The PI will evaluate each AE and SAE for safety and causality. All AEs and SAEs will be recorded and reported to the IRB on a regular basis.

8.3.6 REPORTING EVENTS TO PARTICIPANTS

Subjects, their study partners, and, if so desired by the subject and their study partner, the subjects' primary care physician will be informed of all AEs and SAEs as per GCP guidelines.

9 STATISTICAL CONSIDERATIONS

Initially, baseline variables and outcomes (Clinical Global Impression of Change, Stanford Sleepiness Scale) will be summarized using descriptive statistics for each intervention. For the primary comparison of outcomes between visits 1 and 2, general linear mixed models will be constructed. GLMMs are an excellent means of accounting for clustering (correlation) of observations within subjects over time, which naturally occur as a part of crossover designs such as this. The models for CGIC, SSS and SIB-8 will include main effects for sequence (intervention order), period (a subject's first or second trial), and intervention (music vs. nature sounds), along with random subject effects. Since this is a pilot study of n=10, the focus will be on estimating group differences as opposed to formal hypothesis testing. The estimates provided by the GLMMs will be vital for designing a future more definitive crossover trial.

For fMRI analysis based on data from Visit 3, we will use analytic methods similar to those used in our prior publications of functional network connectivity²⁵⁻²⁹ and similar to other studies³⁰. Briefly, following fMRI preprocessing and nuisance signal regression, residual time series from each of 294 brain regions (nodes) will be submitted to partial correlation to establish the connectivity between each pair of nodes in the network, controlling for connectivity of all other nodes. These pair-wise correlations then serve as edge weights in the calculation of graph-theory measures like diversity coefficient.

The Brain Connectivity Toolbox (BCT)³¹ will be used to calculate diversity coefficient after establishing the community structure in each participant using modularity and consensus functions. Modularity will be run 1000 times for each subject, and the consensus community structure, as implemented in the BCT, will be determined. The diversity coefficient of the auditory cortex will be the primary measure of interest. The higher the diversity coefficient of the auditory cortex, the greater the spread of information to other networks in the brain [JL2] [a3]. Visualization of the connectivity of the auditory cortex as measures by diversity coefficient is expected to reveal greater connectivity with frontal and fronto-parietal networks associated with arousal in the preferred music condition compared to continuous resting state or nature sound conditions. A separate GLMM will then be used to determine whether the diversity coefficient differs by intervention; this model will include main effects for

sequence (intervention order) and intervention (because there is only one MRI session, period is not applicable), along with random subject effects.

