- 3. The areas of the brain that are initially activated by music do not seem to be affected by neurodegenerative disorders or are only affected in the late stages of these disorders, including AD. This

phenomenon offers a unique opportunity to use these "unaffected brain areas" as an initial point for brain activation.

4. Further supporting the concept of expansion of music activation in the brain (perhaps through the process of entrainment) are preliminary studies supporting music as a strong stimulator of brain activity in cognitively impaired subjects. A number of anecdotal reports and uncontrolled trials have provided optimism for the use of music to stimulate brain activity in patients suffering from neurodegenerative disorders⁴.

Based upon both literature review and experiential interventions with music and subjects with degenerative brain illness, this research team has identified the following hypotheses:

Using a crossover design, stimulation with preferred music will lead to improvement in global clinical measures as assessed by CGIC and a higher level of arousal compared to stimulation with nature sounds in the same subjects. Stimulation with preferred music as opposed to nature sounds in the same subjects will demonstrate greater connectivity with brain networks associated with arousal as demonstrated by fMRI.

Below we summarize the scientific background in more detail.

1. Music is a strong stimulator of brain activity.

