Auditory acuity will be evaluated to determine the intensity of the sound the subjects are exposed to. Specifically, the level of sound the subjects are exposed to will be calibrated in relation to their hearing abilities in order to assure a similar level of music stimulation in all subjects. We will use a well-established hearing test, pure-tone audiometry, to perform this evaluation on the study population²⁴.

The goal of the fMRI scans is to determine whether the preferred music intervention enhances connectivity with brain networks associated with arousal as compared to pure resting state and nature sounds. The primary outcome measure for connectivity will be a measure of entropy or spread of information from the auditory cortex to other parts of the brain.

Our chosen MMSE score for the study is 5-20 points. The MMSE is a test designed to evaluate basic cognitive functions and is often utilized to gauge the level of impairment in patients with AD. The MMSE is scored is 0-30, with scores of 20 to 24 suggesting mild dementia, scores of 13 to 20 suggesting moderate dementia, and scores of less than 12 suggesting severe dementia.

On average, the MMSE score of a person with AD declines about two to four points each year. As stated, a MMSE score of 20 usually reflects a patient in the moderate stages of the disease where brain degeneration starts to become more pronounced, but where we believe auditory areas remain almost intact. The lower score of 5 reflects the severe stages of the disease where we believe even auditory areas of the brain engaged in music activation will start to be affected, thus scores below 5 will be excluded.

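### The diversity coefficient measures how evenly auditory connections are distributed over modules, so alone it cannot support the fMRI claim of stronger coupling to frontal and fronto-parietal arousal networks

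*Combined protocol and SAP*

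**What the plan says.** Section 9 obtains partial correlations between 294 brain regions in each scan. It then says: "These pair-wise correlations then serve as edge weights in the calculation of graph-theory measures like diversity coefficient". The modules come from "establishing the community structure in each participant using modularity and consensus functions". One summary is singled out: "The diversity coefficient of the auditory cortex will be the primary measure of interest". Its stated meaning is "The higher the diversity coefficient of the auditory cortex, the greater the spread of information to other networks in the brain". The only fMRI model in the section is a mixed model asking whether this coefficient differs by intervention.

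The question put to the scans is worded differently. Section 2.2 hypothesises "greater connectivity with brain networks associated with arousal as demonstrated by fMRI". Section 4.2 gives the goal as finding out "whether the preferred music intervention enhances connectivity with brain networks associated with arousal", and describes the measure as "a measure of entropy or spread of information from the auditory cortex to other parts of the brain". Section 9 says that the visual display, itself based on the coefficient, "is expected to reveal greater connectivity with frontal and fronto-parietal networks associated with arousal in the preferred music condition".

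No section plans auditory-to-fronto-parietal strength, or total strength outside the auditory module, as an outcome.

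**The concern.** The hypothesis concerns an amount of coupling to particular networks. The modelled measure concerns how evenly coupling is shared among all modules. The two can move together, but need not.

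This matters because the synopsis and Section 3 both place the fMRI network endpoint under the primary objective, and Section 2.2 expects the scans to validate the clinical findings. A higher coefficient under music could be reported as stronger engagement of arousal networks when the auditory module had merely become less tightly coupled within itself. A flat or lower coefficient could be reported as no engagement when the target link had grown. Section 9 also wants the model estimates to inform a later, more definitive trial, so an estimate with the wrong meaning would carry forward.

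**Working it through.** The plan gives no numerical value for this measure, so there is no figure to reproduce. The check is of what the coefficient responds to.

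**Inputs.** From the documents: the measure is an entropy (Section 4.2), computed from pairwise connection weights over data-derived modules (Section 9). Assumed: the normalised Shannon form, which is what the named coefficient denotes but which the documents do not print; inclusion of the own module in the sum; five modules, held fixed; positive strengths. The strengths are illustrative because the documents give none.

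**Formula.** Let s_u be the auditory cortex's strength to module u, S the sum of all s_u, p_u = s_u / S and m the number of modules. Then

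h = −Σ p_u ln p_u / ln m.

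Only shares enter, so any common multiplier cancels.

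**Direction.** Write H = h ln m. Then dH/ds_u = −(ln p_u + H) / S. The coefficient therefore falls as link u grows whenever p_u > exp(−H), and rises when p_u is below that value. The same rule applies to the own-module link: if its share is above exp(−H), weakening it raises h.

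**Worked start.** For [6,1,1,1,1] (own module, target network, three others), p = 0.6 and four times 0.1. Then H = 0.3065 + 0.9210 = 1.2275, and h = 1.2275 / ln 5 = 1.2275 / 1.6094 = 0.763.

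| Profile | Change | Target link | Total outside | h |
|---|---|---|---|---|
| [6,1,1,1,1] | start A | 1 | 4 | 0.763 |
| [3,1,1,1,1] | own module halved, outside unchanged | 1 | 4 | 0.917 |
| [3,0.9,0.9,0.9,0.9] | own module halved, every outside link −10% | 0.9 | 3.6 | 0.898 |
| [12,2,2,2,2] | every link doubled | 2 | 8 | 0.763 |
| [6,2,1,1,1] | target doubled | 2 | 5 | 0.804 |
| [6,8,1,1,1] | target eight-fold | 8 | 11 | 0.759 |
| [4,3,1,1,1] | start B | 3 | 6 | 0.881 |
| [4,5,1,1,1] | target 3 to 5 | 5 | 8 | 0.840 |

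For start B, exp(−H) = 0.242 and the target's share is 0.300. It is above the threshold, so the fall is as the derivative predicts.

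**Dependence on the own module being counted.** If it is left out, outside links going from (3,1,1,1) to (1,1,1,1) still raise h from 0.896 to 1.000, although the largest link has shrunk to a third.

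**Range over assumed profiles.** In 100,000 random profiles per setting, with own-module strength multiplied by 1, 3 and 6:

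- a 25% weaker own link, nothing else changed, raised h in 30%, 77% and 92%;
- a 25% stronger target link lowered h in 41%, 22% and 10%.

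These percentages describe the assumed profiles, not the patients.

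**The case against.** The strongest reply is that Section 4.2 uses spread as another word for entropy. On that usage, reading a higher coefficient as greater spread is true by definition. This stands. A reader might infer that the quoted sentence is simply wrong; the documents do not support that. The gap lies in the next step, from evenness to stronger connectivity with particular networks.

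A second reply is that the plan's expected direction often holds. This also stands. From start A, moderate growth of the target link raises h, and h drops below its start only after about 7.8-fold growth. From a flatter start (0.4 and four at 0.15) the crossover is about 2.35-fold. A reader might infer that the sign will usually be reversed; nothing in the documents shows that.

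Third, the formula and the handling of negative weights are not printed, and the examples hold modules fixed although Section 9 estimates them from data. These are fair limits on the numerical examples. They do not remove the basic property that a normalised entropy of shares ignores amount and does not identify the network reached.

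Finally, this is a pilot of 10 focused on estimation, with no decision rule tied to the coefficient. That limits the consequence to interpretation. The planned visual display is only a partial safeguard, because it too is based on the coefficient.

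**Conclusion.** The concern holds in this form: the only modelled fMRI measure cannot, by itself, show the stronger coupling to frontal and fronto-parietal arousal networks that Sections 2.2, 4.2 and 9 set out to demonstrate.

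The coefficient can rise with no growth outside the auditory module, or even with shrinkage there. It ignores a uniform change in strength. It can fall when the target link grows. The first is the likelier problem if the own module dominates; the last becomes more common as the profile flattens. The sizes rest on assumed strengths, five fixed modules and the standard normalised entropy, and both directions are statements of what can happen.

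The change is worth making before analysis, because it lets the trial answer its own fMRI question at almost no cost.

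**What to change.** 1. Keep the diversity coefficient, but reword its interpretation in Section 9: a higher value means that the auditory cortex's connections are more evenly distributed over modules.
2. From the same matrices, compute the auditory cortex's connection strength to the frontal and fronto-parietal nodes, using node sets fixed in advance and identical for all three scans.
3. Report within-module and total between-module strength beside it, with positive and negative weights handled separately. State whether modules are re-estimated for each scan.
4. Fit the mixed model already planned for the coefficient to these strengths. Base any statement about stronger coupling to arousal networks on the auditory-to-frontal/fronto-parietal strength, not on the coefficient alone.

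Total between-module strength should not serve as the test of that statement. If outside links go from (0.1, 0.1, 0.1, 0.1) to (0.05, 0.3, 0.1, 0.1), the total rises from 0.40 to 0.55 while the first link, taken as the target, halves.

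The cost is a few lines of code and a few more fMRI outcomes to report in a pilot of 10. No further scans, visits or participants are needed.
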